#### 3.3 Withdrawal Criteria

Patients may voluntarily withdraw from the study at any time for any reason without prejudice. Patients will be withdrawn from the study for any of the following reasons:

- Adverse event
- Noncompliance with the protocol
- Lost to follow-up
- Physician decision
- Study terminated by sponsor
- Withdrawal by subject
- Other

Treatment may be terminated but patient may be still followed in the study for the following reasons:

- Adverse event
- Physician decision
- Pregnancy
- Death
- Lost to follow-up
- Study terminated by sponsor
- Withdrawal by subject
- Protocol deviation
- Other

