# Study ANK-700-01 in Relapsing-Remitting Multiple Sclerosis

a All patients should be contacted by site staff 1 day before each study visit for assessment of COVID-19 signs and symptoms.

- b Early termination visit only if patient discontinues within 28 days of dosing.
- c On D1 patients will be observed in the clinic/hospital unit for 8h after completion of IV infusion and followed up with by phone following discharge 24 hours after dosing.
- d Pes will also be conducted on study as clinically indicated.
- e Includes weight at screening only.
- f Pregnancy test at screening must be serum; serum or urine tests are acceptable on D1, D4, and D7 prior to dosing. Screening and dosing day pregnancy tests must be negative before study drug is administered. Additional pregnancy monitoring per local guidelines may be implemented.
- g Samples/measurements taken pre-dose.
- h Vital signs include pulse rate, temperature, and diastolic and systolic blood pressure.
- i In the event of a suspected disease relapse, an unscheduled MRI and EDSS assessment may be performed if deemed clinically necessary.
- j The screening MRI must be performed ≥ 10 days prior to dosing on D1. For re-screening, the MRI only needs to be repeated if the previous assessment has been completed >3 months of scheduled dosing or if a relapse has occurred since last assessment
- k The MRI at D22 may be performed up to 3 days before the D22 visit.
-  The MRI at D90 may be performed within 2 weeks of the scheduled D90 visit.
- m On D1, patients will be observed in the clinic for 8 h after completion of IV infusion.
- n On D4 and D7, patients will be observed for 4 h after completion of IV infusion.
- o On D1, 1 PK sample will be taken pre-dose (≥ 5 min prior to infusion), with all subsequent PK samples taken after the end of infusion (EOI) at the following time points: EOI 0 (+2) min, EOI 7 (±2) min, EOI 15 (±2) min, EOI 30 (±5) min, EOI 1 h (±5 min), EOI 2 h (±5 min), EOI 3 h (±5 min), EOI 4 h (±5 min), EOI 6 h (±5 min) and EOI 8 h (±5 min). PK samples to be taken from the arm that did not receive the infusion. The exact date and time of each sample collection must be recorded for all collected samples.

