#### 4.10. TREATMENT DISCONTINUATION

Patients will be discontinued from treatment for any of the after reasons:

- An AE that requires permanent discontinuation of study treatment\*
- Noncompliance with the protocol

Study ANK-700-01 in Relapsing-Remitting Multiple Sclerosis

- Investigator decision
- patient becomes pregnant
- patient death
- patient lost to follow-up
- termination of the study by the Sponsor
- voluntary withdrawal of consent by patient

The reason for treatment discontinuation will be documented.

All patients will have a final follow-up approximately 6 months (D182  $\pm$  7) after the single dose of ANK-700 in Part A and approximately 1 year (D365  $\pm$  14) after the first dose in Part B unless the patient withdraws from the study prematurely (Section 4.11).

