### 7. CONCOMITANT MEDICATIONS

### 7.1. PROHIBITED CONCOMITANT THERAPIES

During the first 3 months of the study period, any DMTs not listed as a permitted concomitant therapy to treat RRMS (Section 7.2) or other investigational agents are prohibited, including biologic or nonbiologic therapies. All vaccines are prohibited within 4 weeks before dosing and for 2 months after dosing. Patients should avoid taking biotin-containing dietary supplements throughout the duration of the study.

Patients previously treated with any of the following DMTs must adhere to the washout periods outlined below:

- 3-month washout
  - glatiramer acetate, parenteral steroids, or adrenocorticotropic hormone,
     β-interferon, plasma exchange
- 6-month washout
  - fingolimod, ozanimod, or siponimod
- 12-month washout
  - cytotoxic agents (including but not limited to cladribine, mitoxantrone, cyclophosphamide, azathioprine, and methotrexate), laquinimod, teriflunomide, or IV gamma globulin
- 24-month washout
  - mAb therapy (including natalizumab, daclizumab, rituximab, and ocrelizumab)

After patients have completed the 3-month visit (D90), they may receive alternative DMTs for their MS if judged clinically appropriate by their treating physician or the Investigator.

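### SAP 3.3 ends study participation for an adverse event or noncompliance, contrary to protocol 4.10 and 4.11 and to its own second list; separately, the early-termination visit lapses after 28 days and never includes an EDSS

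*SAP*

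**What the plan says.** SAP 3.3 holds two lists. The first opens with "Patients will be withdrawn from the study for any of the following reasons" and includes adverse event and noncompliance. The second opens with "Treatment may be terminated but patient may be still followed in the study for the following reasons" and includes adverse event again, along with protocol deviation.

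Protocol 4.10 (Treatment Discontinuation) covers stopping treatment. Its reasons include "An AE that requires permanent discontinuation of study treatment" and "Noncompliance with the protocol". It then provides a final follow-up for all patients at D182 in Part A and D365 in Part B, "unless the patient withdraws from the study prematurely", and points to 4.11 for that exception. Protocol 4.11 (Study Withdrawal) gives five reasons: investigator's decision, death, loss to follow-up, termination by the sponsor, and withdrawal of consent.

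On exit assessments, footnote b to protocol Tables 1 to 3 reads "Early termination visit only if patient discontinues within 28 days of dosing". In those tables the Early Term. column has no mark in the EDSS or MRI row. SAP Appendix 1 repeats the footnote and the same blanks. SAP section 10 analyses withdrawn patients up to their last evaluation.

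**The concern.** The primary endpoint is the incidence and severity of TEAEs from first dose to the final follow-up visit. A rule that removes patients from the study because they had an AE would shorten observation for a reason tied to the outcome. In a first-in-human study with 3 patients per single-dose cohort and 8 per multiple-dose group, one such patient matters.

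The subject matter adds weight. Protocol 1.2 notes that earlier work with myelin-derived altered peptide ligands saw disease exacerbation or more inflammatory lesions. Protocol 11.1.1 counts worsening MS as an AE, and the synopsis names EDSS and MRI as the means of assessing relapse. A patient leaving with a neurological complaint is one for whom a closing EDSS would be informative, and the schedule provides none.

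**Working it through.** **Planned follow-up reproduced.** Screening 28 days + 182 = 210 (Part A); 28 + 365 = 393 (Part B). Both match the stated maximum durations, so D182 and D365 are the right end points for the counts below.

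**The lists side by side.**

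| Reason | Protocol 4.10 (stop treatment, keep follow-up) | Protocol 4.11 (leave study) | SAP 3.3, first list (leave study) | SAP 3.3, second list (follow-up possible) |
|---|---|---|---|---|
| Adverse event | Yes, if it requires permanent discontinuation | No | Yes | Yes |
| Noncompliance | Yes | No | Yes | Not by that name; protocol deviation is listed |
| Investigator or physician decision | Yes | Yes | Yes | Yes |

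Of the seven reasons in the first SAP list, six (all but noncompliance) also appear in the second. The SAP therefore does not determine what happens to a patient with an AE. Its first list is mandatory in wording, whereas protocol 4.10 keeps the same patient to the final visit. The first list also lacks the qualifier that the AE must require permanent discontinuation.

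**Reach of the early-termination visit.** Footnote b does not say whether the 28 days run from the first or the last dose.

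- Part A, dose on D1: window ends D1 + 28 = D29. Days without a closing visit: 182 − 29 = 153; 153/182 = 84%.
- Part B, counted from D1: 365 − 29 = 336; 336/365 = 92%.
- Part B, counted from the last dose on D7: window ends D35; 365 − 35 = 330; 330/365 = 90%.

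**Last scheduled assessment for an exit after that window and before D90.**

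- EDSS days are D1, D15, D90, D182 in Part A (gaps 14, 75, 92 days) and D1, D22, D90, D182, D365 in Part B (gaps 21, 68, 92, 183 days).
- The last scheduled EDSS is therefore at D15 in Part A and D22 in Part B. The D29 and D43 visits have none.
- Post-dose MRI is scheduled at D15 only in Part A, so a later Part A exit misses no scheduled scan. In Part B it is at D22 and D90. The D90 scan may be done within two weeks of that visit, so one could exist from 90 − 14 = D76. Before that, D22 is the last.

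**What one lost patient means in a Part B dose group.** One unrecorded worsening among 8 moves the observed proportion by 1/8 = 12.5 points. For an event arising only after exit, the chance of seeing at least one case is 1 − (1 − p)^n. The documents give no event rates, so p is assumed:

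| Assumed p | n = 8 | n = 7 |
|---|---|---|
| 5% | 33.7% | 30.2% |
| 10% | 57.0% | 52.2% |
| 20% | 83.2% | 79.0% |
| 30% | 94.2% | 91.8% |

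The loss is 2 to 5 percentage points per patient.

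**The case against.** The strongest reply is that SAP 3.3 does not govern conduct. Protocol section 12 gives the final SAP precedence on methods, and SAP section 1 supersedes the protocol's statistical considerations; neither clearly covers who leaves the study. The SAP lists, each ending in an open category, may only be reason codes for the disposition table. Read literally, the second list would continue follow-up after death. Sites may well follow protocol 4.11. This stands, and it is why the loss is conditional. It does not remove the contradiction: SAP 8.8.1 plans a listing of TEAEs leading to study discontinuation, so the SAP does expect AE-led exits.

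It is also fair that the safety record has other supports. AEs are followed until resolved, back to baseline, stable or chronic (protocol 11.2.1). Suspected relapse should be assessed by EDSS and/or MRI as appropriate (protocol 11.1.2), outside the schedule if need be. A treated patient stays in the All-Treated set, and recorded TEAEs stay in the tables.

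Three stronger readings are tempting and fail:

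- **That starting a non-permitted disease-modifying therapy before D90 leads to withdrawal.** Protocol 7.1 states no such consequence. The link needs the start to be classed as noncompliance, while protocol deviation sits in the SAP list that allows follow-up.
- **That worsening patients leave the safety record.** Their data to the last evaluation remain; what is lost is later.
- **That a D90 table would be biased in a known direction.** No EDSS summary is planned; protocol 12.5 only lists EDSS. The by-visit MRI summary in SAP 8.8.7 could lose a patient, but nothing in the documents indicates which group would be favoured.

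**Conclusion.** Two points hold. First, SAP 3.3 conflicts with protocol 4.10 and 4.11, and with itself, on whether an AE or noncompliance ends study participation. If its first list were followed, later TEAEs and scheduled EDSS and MRI would be lost because of an AE; cumulative TEAE counts would keep everything recorded before exit. Secondly, no schedule has an EDSS or MRI at early termination, even inside the 28 days, and after that window there is no closing visit at all. That covers 84% of follow-up days in Part A and 90% to 92% in Part B, depending on which dose starts the count.

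The D15 and D22 statements assume that no unscheduled relapse assessment was done. The detection figures rest on assumed event rates and on one patient lost from 8. The number of patients affected cannot be estimated from the documents. This should be corrected, but it does not undermine the design.

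**What to change.** 1. In SAP 3.3, remove adverse event and noncompliance from the study-withdrawal list, so that it agrees with protocol 4.11 and these patients remain in safety follow-up to D182 or D365 as protocol 4.10 provides.
2. In protocol Tables 1 to 3 and SAP Appendix 1, add EDSS to the Early Term. column.
3. Reword footnote b so that the visit also applies to study exits after 28 days. This also removes the need to decide which dose starts the count.

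These changes affect data collection only; rules for stopping treatment are untouched. The cost is wording in two documents and, for the few who leave early and can attend, one exit visit using an assessment already in the study. No exit MRI is added, so the MRI gap stays; unscheduled imaging for suspected relapse remains available.

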#### 4. CLINICAL PROCEDURES AND ASSESSMENTS

The assessments collected in the study are outlined in Appendix 1 Table 1 (Part A), Table 2 (Part B, Cohort 4) and Table 3 (Part B, Cohort 5).

#### 5. STUDY OBJECTIVES

Below is an outline of the study objectives

#### 5.1 Primary

 Assess safety and tolerability of escalating doses of ANK-700 in patients with RRMS

## 5.2 Secondary

• Evaluate the PK of escalating doses of ANK in patients with RRMS

#### 6. ASSESSMENTS

## 6.1 Safety Assessments

The safety and tolerability of ANK-700 will be assessed by AE and other safety assessments as detailed in Appendix 1 Table 1 (Part A), Table 2 (Part B, Cohort 4) and Table 3 (Part B, Cohort 5).

#### 6.1.1 Adverse Events (AE)

An AE is defined as any untoward medical occurrence associated with the use of a drug, or with study participation, whether or not consider related to study treatment. An AE can

therefore be any unfavorable and unintended sign (eg, an abnormal laboratory finding), symptom, or disease temporally associated with the use of the medicinal product, whether or not considered related to the medicinal product.

AEs include worsening of a pre-existing medical condition, including MS, as well as Clinically Significant (CS) changes from baseline laboratory values/conditions. Worsening of the preexisting medical condition (eg, diabetes, hypertension) means that it has increased in severity, frequency, and/or duration, and/or has an association with a significantly worse outcome. A pre-existing condition that has not worsened during the study is not considered an AE.

All AEs are collected from the time of signing of Informed Consent Form (ICF) through the final Follow-Up Visit/phone. Adverse events will be coded using the Medical Dictionary for Regulatory Activities (MedDRA) Version 23.1 (MedDRA Sep 2020) or higher. Ongoing AEs considered at least possibly related to ANK-700 treatment should be followed until resolution, return to baseline, or are considered stable or chronic.

## **6.1.2** Treatment Emergent Adverse Events (TEAE)

TEAEs are defined as AEs that emerge or worsen in the period from the first dose of study treatment to the final Follow-Up Visit/phone call after the last dose study drug. The incidence and severity of TEAEs as assessed by the CTCAE v5.0 or higher is considered the primary endpoint.

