# **6.1.8.** Brain Magnetic Resonance Imaging

As outlined in Table 1 and Table 2, screening and post-dose brain MRIs will be performed. Scans will be performed by trained and certified MRI technicians. The MRI will include the acquisition of scans at each time point with and without IV administered gadolinium contrast enhancement.

The following time windows apply:

- "Screening/baseline" MRI should be performed on or after the Screening Visit, but ≥ 10 days before the D1 visit.
- The MRI obtained for the Part A D15 Visit and Part B D22 Visit should be performed up to 3 days before or on the scheduled visit day.
- MRI at Part B visit D90 should be performed within 2 weeks of the scheduled visit.

MRIs will be performed for assessment of safety only and will be reviewed locally.

Study ANK-700-01 in Relapsing-Remitting Multiple Sclerosis

If a relapse occurs at the time of a scheduled MRI, the MRI should be obtained before initiation of corticosteroid therapy or the MRI should be postponed by 1 month.

If the screening MRI has been completed within 3 months of scheduled dosing it would not need to be repeated as long as the screen fail is not due to MS relapse. If the patient needs to re-screen due to experiencing an MS relapse during the screening period, the patient must wait at least 28 days from the relapse resolution and then a new screening MRI should be obtained (and the rescreening MRI must be at least 28 days from last MRI assessment).

All patients with new neurological symptoms suggestive of MS relapse should have an MRI performed (which may include the spinal column) during an unscheduled visit, if clinically necessary, but before the initiation of steroids (see Section 11.1.2).

Additional details on MRI acquisition procedures are described the imaging acquisition guidelines.

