# **6.2.** SAFETY FOLLOW-UP VISIT

All patients in Part A will have a final Follow-Up Visit at D182 ( $\pm 7$  days), 6 months after the single administration of ANK-700.

All patients in Part B will have a final Follow-Up Visit at D365 ( $\pm 14$  days), approximately 1 year after the first administration of ANK-700.

Ongoing AEs considered at least possibly related to ANK-700 treatment should be followed until resolution, return to baseline, or are considered stable or chronic.

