After patients have completed the 3-month visit (D90), they may receive alternative DMTs (Disease modifying Therapy) for their MS if judged clinically appropriate by their treating physician or the Investigator. Summary statistics for observations after 90 days may be presented in a sample size report, stratified by medication, if sample size permits.

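### Part B TEAE tables run to D365 although new DMTs are allowed after D90; add a supportive table restricted to the period before D90 or new-DMT start

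*SAP*

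**What the plan says.** SAP 6.1.2 gives this definition of TEAEs: "AEs that emerge or worsen in the period from the first dose of study treatment to the final Follow-Up Visit/phone call". On their role it states: "The incidence and severity of TEAEs as assessed by the CTCAE v5.0 or higher is considered the primary endpoint". Protocol 6.2 fixes the end of that period. For Part A, "All patients in Part A will have a final Follow-Up Visit at D182" (±7 days); for Part B, "All patients in Part B will have a final Follow-Up Visit at D365" (±14 days). Dosing is one infusion in Part A and three infusions, the last on D7, in Part B (Protocol 4.3).

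The bar on other DMTs in Protocol 7.1 is limited in time. It begins "During the first 3 months of the study period, any DMTs not listed as a permitted concomitant therapy to treat RRMS", and the section closes: "After patients have completed the 3-month visit (D90), they may receive alternative DMTs for their MS". This is left to clinical judgement.

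SAP 8.8.1 lists the Part B TEAE tables: overall, SOC/PT, severity, causality, maximum CTCAE grade, and serious. None is split by period, cut at D90, or censored at the start of a DMT. SAP 8.8 counts a patient once per event, and 8.8.1 uses the worst recorded grade. The only text on data after D90 is in SAP 8.3: "Summary statistics for observations after 90 days may be presented in a sample size report, stratified by medication, if sample size permits".

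For imaging, Protocol 6.1.8 and SAP 6.1.9 give the last scheduled Part B scan a wide window: "MRI at Part B visit D90 should be performed within 2 weeks of the scheduled visit".

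**The concern.** SAP 3.1 gives a safety comparison of ANK-700 with placebo as the reason for the 24 patients in Part B. Two features of the primary tables weaken that comparison.

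- **Window length.** A patient counts once however many events occur. Background AEs over a year fill both arms, so an excess that appears soon after dosing becomes harder to see.
- **New DMTs.** For about three quarters of the window, AEs can arise under a drug that is not under study. Starting one is a decision made after dosing, so randomization does not balance it, and SAP 9 plans no covariate adjustment. A later DMT-related event can also set a patient's maximum grade.

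No planned table shows TEAE incidence against placebo over the period when other DMTs were still barred. A Part B D90 scan may also be taken after the D90 visit, and so after a new DMT has begun. SAP 8.8.7 has no rule for identifying such scans.

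**Working it through.** **1. The plan's own figures.** Protocol 13.9 gives maximum participation as about 210 and 393 days: 28 + 182 = 210 and 28 + 365 = 393. Part B: 2 × 12 = 24 = 8 + 8 + 8. All reproduce. There is no power calculation to check; SAP 3.1 says none was done and SAP 8 plans no test.

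**2. Share of the TEAE window open to new DMTs**, (end − 90)/end:

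- Part A: 92/182 = 50.5%. With visit windows: (175 − 97)/175 = 44.6% to (189 − 83)/189 = 56.1%.
- Part B: 275/365 = 75.3%. With visit windows: (351 − 97)/351 = 72.4% to (379 − 83)/379 = 78.1%.

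**3. Dilution from window length alone.** The documents give no AE rates, so all rates here are assumptions. Let b be the background probability of any TEAE by D90 with constant hazard, and q the probability that ANK-700 adds an early event. Then background by day T is p(T) = 1 − (1 − b)^(T/90), and the difference between arms is RD(T) = q × (1 − p(T)). With q = 0.30:

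| b (by D90) | p(365) | RD at D90 | RD at D365 |
|---|---|---|---|
| 30% | 76% | 21 points | 7.1 points |
| 50% | 94% | 15 points | 1.8 points |
| 70% | 99% | 9 points | 0.2 points |

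No DMT term enters this formula.

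A milder case takes 50% background by 12 months and q = 0.40. Background by D90 is 1 − 0.5^(90/365) = 15.7%, so RD is 0.40 × 0.843 = 33.7 points at D90 and 0.40 × 0.50 = 20.0 points at D365. Across 12-month backgrounds of 30% to 90% and q of 0.25 to 0.40, RD runs from 14 to 37 points at D90 and from 2.5 to 28 points at D365. For any non-zero background the difference shrinks; how far depends on the rate.

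**4. Adding DMT use to the milder case**, again with assumed rates. If a share s of both arms starts a DMT and half of the starters have a TEAE from it, RD at D365 is 0.40 × 0.50 × (1 − 0.5s): 17.5 points for s = 25% and 15.0 for s = 50%. Window length thus removes 33.7 − 20.0 = 13.7 points, and DMT use a further 2.5 to 5. If the share differs by arm (25% versus 50%) and ANK-700 has no effect, a spurious difference of 0.50 × 0.5 × 0.25 = 6.25 points appears, in either direction.

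**5. Precision.** For 65% versus 50% with 16 versus 8 patients, the standard error is √(0.65 × 0.35/16 + 0.50 × 0.50/8) = 0.213. An approximate 95% interval is ±42 points.

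**6. What the other planned outputs cover.**

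| Output | Why it is not the missing table |
|---|---|
| Drug-related counts (both parts) and causality table (Part B), SAP 8.8.1 | Full window; depend on investigator attribution |
| DLT listing, SAP 6.1.6 and 8.8.1 | Stops at D15 or D22; only Grade 3 or higher, or unresolved Grade 2 |
| AE listings with onset dates (8.8.1); medication listings with dates (8.3) | Contain what is needed, but the reader must sort by hand |
| Post-D90 summary, SAP 8.3 | Optional, output undefined, names no TEAE table, describes the later period |

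**The case against.** The strongest reply is that long follow-up is deliberate. ANK-700 is meant to induce immune tolerance, and Protocol 1.2 notes that earlier work with altered peptide ligands saw disease exacerbation, so a half-life under 7 minutes does not limit the period of interest. This stands: the full window is legitimate and should stay.

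It can also be said that any TEAE is the measure that saturates fastest. Specific preferred terms, higher grades and serious events lose less contrast. Investigators classify relatedness, so AEs with another clear cause should fall outside the drug-related counts. This also stands in part, but those counts rest on judgement, whereas the placebo arm offers a comparison that does not.

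Finally, with 16 versus 8 patients a 15-point difference could not be resolved in either window. That is correct, and it limits the benefit to clearer description.

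A reader might infer more than the documents support:

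- *That new DMTs cause the fall from 15 to 2 points.* They do not enter that calculation, and no DMT-start rate is given.
- *That most of the window is exposed in both parts.* This holds for Part B; Part A is about half, and below half for some visit timings.
- *That SAP 8.3 is the only safeguard.* The causality, DLT and listing outputs also help.
- *That D90 scans taken after a DMT start should be dropped.* That could selectively remove patients who are worsening.

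**Conclusion.** The point holds for Part B as a modest improvement to the SAP. About 75% of the primary TEAE window is open to AEs under a new DMT, and no planned table gives the placebo comparison for the DMT-restricted period. An early excess is diluted in the full-window any-TEAE count. The direction holds for any non-zero background rate; the size rests on assumed rates and is smaller with lower background rates, specific terms or higher grades. Most of the dilution is due to window length. The DMT contribution cannot be quantified from the documents; step 4 shows only what it could be.

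In Part A there is no placebo contrast to lose, so a listing flag is enough. The MRI point is also confined to Part B, because the last scheduled Part A scan is at D15. No hypothesis is tested, so no error rate or power is affected.

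**What to change.** - **SAP 8.8.1, Part B:** keep the full-window tables as primary. Beside them add the overall, SOC/PT and maximum-grade TEAE tables restricted to onset from first dose to the earlier of the D90 visit or the start of any new DMT. Define a new DMT as one not in use at study entry, so that continued fumarate does not trigger the cut. State the cut-off day to use if the D90 visit is missed.
- **SAP 8.8.1, both parts:** flag in the AE listings every AE with onset after a new DMT start.
- **SAP 8.3:** replace the optional sentence on observations after 90 days with a reference to this defined output.
- **SAP 8.8.7, Part B:** flag in the MRI listing any D90 scan taken after a new DMT started; do not exclude it.

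The AE onset and medication dates are already collected, so the cost is a few extra tables and flags. SAP 10.2 moves a partial medication start date to the first of the month or year, which can place the cut too early; such cases should be footnoted. The restricted tables are conditioned on a post-dose decision, so label them supportive; they do not replace the full-window primary tables.
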